8.5. Study size

The primary endpoints of this study in patients with adv/mRCC are PFS and TTF for patients receiving AXI in 2nd line and the combined PFS and TTF for patients receiving the SU-AXI sequence. In this non-interventional real life study, the objective is only descriptive and the sample size will rely on the precision of the estimate.

The expected precision of the median PFS can be calculated with the Greenwood's formula. The formula provides an estimate of the variance of S(t) (Kaplan-Meier estimate) as follows:

$$\hat{Var}[\hat{S}(t)] = [\hat{S}(t)]^2 \sum_{j:t_i \leq t} \frac{d_j}{n_j(n_j - d_j)}$$

where tj is the times of events, dj the number of events at these times and nj the sample size at risk.

Assuming the absence of right-censoring before the median survival and the occurrence of a single event for each event time, Greenwood's formula for median survival can be simplified as follows:

$$\hat{Var}[\hat{S}(t)] = \frac{0, 5^2}{n}.$$

The different variances and CI of S(t) can therefore be calculated as a function of n and accuracy.

		Variance	
s(t) ²	n	$(s(t)^2/n)$	Accuracy
	150	0.001666667	0.080
	175	0.001428571	0.074
	200	0.00125	0.069
	225	0.001111111	0.065
0.25	250	0.001	0.062
	300	0.00083	0.056
	350	0.0007143	0.052

Table 2: sample size and accuracy of PFS

Inclusion of 350 patients with the SU-AXI sequence will allow demonstration of median progression free survival as well as time to treatment failure with an accuracy of 5.2%.

The SU-AXI 350-patient sample is expected to comprise two thirds of patients enrolled in the AXI 2nd line pool (approx. 225 patients) and one third of patients enrolled in the SU 1st line pool then receiving an AXI 2nd line (approx. 125 patients).

This last group (125 patients) implies initial inclusion of 525 patients in the SU 1st line pool. Based on current EU market research and 2014 forecasts, it is expected that 68% of the SU 1st line pool has a 2nd line treatment (357 patients); and that 35% are expected to initiate 2nd line treatment with AXI (125 patients).

ADONIS is therefore targeting approximately 750 patients: 225 in the AXI pool and 525 in the SU pool. These estimates will allow for an approximate SU-AXI 350- patient group to meet primary outcome objectives and a SU – other 2nd line treatment group of 230 patients to meet secondary objectives.

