Similar to PFS, Kaplan-Meier analyses will be performed for TTF and TSF.

Objective Response Rate (ORR)

ORR is defined as the percentage of patients with confirmed complete response (CR) or confirmed partial response (PR) according to RECIST V1.1, relative to all patients who have baseline measurable disease. Confirmed responses are those that persist on repeat imaging study \geq 4 weeks after initial documentation of response.

Patients who die, progress, or drop out for any reason prior to reaching a CR or PR will be counted as non-responders in the assessment of ORR. A patient, who initially meets the criteria for a PR and then subsequently becomes a confirmed CR, will be assigned a best response of CR.

ORR will be assessed and a 2-sided 95% confidence interval will be provided using the Clopper-Pearson formula.

Overall Survival (OS)

OS is defined as the date from first SU dose to the date of death due to any cause. For patients not experiencing the event, their survival times will be censored at the last date they are known to be alive. Similar to PFS, Kaplan-Meier analyses will be performed for OS. The share of patients alive (OS) at 2 year will be measured for the sequence.

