4. AXITINIB SECOND LINE VISITS

4.1. AXITINIB INITIATION VISIT

Axitinib Initiation Date / / 20 (DD/MM/YYYY)	Patient identifier 🖳				
This visit is performed when the patient starts Axitinib in second line.					
- If the patient was enrolled in the study when Sunitinib started in first lin need an update	- If the patient was enrolled in the study when Sunitinib started in first line, please only fill in sections that need an update				
- If the patient is enrolled at this stage (Axitinib start) please complete ever retrospective section that you will find at the end of the visit	ry section as well as the Sunitinib				
Patient characteristics at Axitinib initiation					
Weight Kg (only for patient enrolled at Sunitinib start),					
ECOG					
Eastern Cooperative Oncology Group (ECOG) available	□ Yes □ No				
If yes,					
□0 □1 □2 □3 □4					
Karnofsky performance status					
Karnofsky status available	☐ Yes ☐ No				
Classification to determine a patient's performance status					
Normal status, no complaints, no evidence of disease	□ 100%				
Minor signs and symptoms of disease	90%				
Normal activities with efforts	□ 80%				
Unable to carry on normal activity, unable to work, able to care for self	□ 70%				
Requires occasional assistance	□ 60%				
Requires nursing and medical care and assistance, not permanently bedridden	□ 50%				
Bedridden, requires special care	☐ 40%				
Severely disabled, requires hospital care					
Requires hospital care and supportive treatment					
Moribund, disease progressing rapidly					
MSKCC risk (second line line) (the definition of 2 nd line MSKCC is	reachable via a click)				
☐ Good ☐ Poor					
□ Intermediate □ NA					

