5.4 SUBGROUPS

Type of 2nd line treatment post SU:

o SU - AXI subgroup

It refers to all patients from the FAS receiving the combined SU-AXI sequence during the observation period. It includes

- patients enrolled at AXI initiation in 2nd line post SU treatment ("SU (retrospective) - AXI")
- and patients enrolled at SU initiation with SU prospective part and receiving AXI in 2nd-line post SU ("SU (prospective)-AXI") (AXI declared as 2nd line at SU discontinuation)

Two different baselines will be considered in the analyses of this subgroup: AXI initiation to explore only the AXI treatment period and SU initiation to consider the SU – AXI sequence.

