The OS will be defined as the time from date of first SU dose to the date of death of any cause. For patients not experiencing the event, their survival times will be censored at the last date they are known to be alive

Variable name	Definition
OS status	Patient will not be censored for the OS analysis (OS status = 1) in the following cases:
	1) Axitinib discontinued due to Death (cf. CRF page 35)
	2) Death reported in Long term Follow-up (cf. CRF page 36)
	 Death reported on the Study Discontinuation form (cf. CRF page 37)
	In all other cases, patient will be censored for the OS analysis (OS status $= 0$).

OS status and OS time will be calculated as detailed below:

Variable name	Definition					
OS time	The overall survival time will be calculated in months as:					
(months)	 (Date of death reported at time of Axitinib discontinuation - Start date of Sunitinib + 1) / 30.44, if case n°1 described above is reported 					
	 (Date of death reported in Long term Follow-up - Start date of Sunitinib + 1) / 30.44, if case n°2 described above is reported 					
	 (Date of death reported on the Study Discontinuation form - Start date of Sunitinib + 1) / 30.44, if case n°3 described above is reported 					
	Else, the overall survival time will be censored as follows:					
	 (Maximum of {All visits dates reported} - Start date of Sunitinib + 1) / 30.44 					
	Note: Start date of Sunitinib will be the one reported:					
	- at time of Sunitinib initiation visit for patients enrolled at SU initiation (cf. CRF page 11 " Therapy started with Sunitinib in 1st line on ")					
	- at time of Axitinib initiation visit for patients enrolled at AXI initiation (cf. CRF page 26 "Therapy started with Sunitinib in 1st line on")					

- Best Response under Axitinib in 2nd line post Sunitinib

Number and percentages of patients by best response (CR, PR, SD or PD) will be presented.

- Objective Response Rate (ORR) under Axitinib in 2nd line post Sunitinib

ORR is defined as the percentage of patients with complete response (CR) or partial response (PR) according to RECIST from the start to the end of Axitinib treatment (cf. CRF page 29).

Patients who die, progress, or drop out for any reason prior to reaching a CR or PR will be counted as non-responders in the assessment of ORR.

All assessments following an assessment of PD will be excluded from the derivation of ORR.

- Clinical benefice Rate (CBR) under Axitinib in 2nd line post Sunitinib

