• Kaplan-Meier estimates (product-limit estimates) will be presented with a summary of associated statistics: number of events, number of censored data, median survival time, Q1 and Q3 survival times and survival rates every 3 months.

The confidence intervals for the median, Q1 and Q3 will also be provided according to Brookmeyer and Crowley (1982)

• The Kaplan-Meier curve will also be presented

Other primary endpoints will be analyzed according to the same methods:

- PFS for the sequence Sunitinib-Axitinib in the SU-AXI subgroup
- TTF under Axitinib in 2nd line post Sunitinib in the SU-AXI subgroup
- TTF for the sequence Sunitinib-Axitinib in the SU-AXI subgroup

Additionally a Cox regression model will run for the PFS under Axitinib in 2nd line post Sunitinib in the SU-AXI subgroup according to the method described in section 8.1 of this document (Strategy of selection of variables in multivariate models). Potential factors to be tested will be defined at time of Data Review Meetings among the ones mentioned in section 6.4 of this document.

Secondary endpoints

TSF for the sequence Sunitinib-Axitinib will be described using the Kaplan Meier method in the SU-AXI subgroup:

• Kaplan-Meier estimates (product-limit estimates) will be presented with a summary of associated statistics: number of events, number of censored data, median survival time, Q1 and Q3 survival times and survival rates every 3 months.

The confidence intervals for the median, Q1 and Q3 will also be provided according to Brookmeyer and Crowley (1982)

• The Kaplan-Meier curve will also be presented

Following secondary endpoints will be analyzed according to the same methods:

- OS for the sequence SU-AXI in the SU-AXI subgroup
- PFS for Sunitinib received in 1st line
- OS for Sunitinib received in 1st line

ORR under Axitinib in 2nd line post Sunitinib will be given with its 2-sided 95% 'exact' Clopper-Pearson confidence interval in the SU-AXI subgroup.

Same analysis will be done for:

- CBR under Axitinib in 2nd line post Sunitinib in the SU-AXI subgroup
- ORR for Sunitinib received in 1st line
- CBR for Sunitinib received in 1st line

Additionally, following analysis will be performed according to MSKCC prognosis classification at Axitinib initiation (good/intermediate/poor) using the Kaplan Meier method:

- PFS under Axitinib in 2nd line post Sunitinib in the SU-AXI subgroup
- ORR under Axitinib in 2nd line post Sunitinib in the SU-AXI subgroup

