- OS for the sequence SU-AXI in the SU-AXI subgroup
- For PFS and OS, the 3 Kaplan Meier curves corresponding to each MSKCC prognosis categories will be printed on a same graph.

Following analysis will be performed according to MSKCC prognosis classification at Sunitinib initiation (good/intermediate/poor) using the Kaplan Meier method:

- PFS for Sunitinib received in 1st line
- OS for Sunitinib received in 1st line
- ORR for Sunitinib received in 1st line
- CBR for Sunitinib received in 1st line
- For PFS and OS, the 3 Kaplan Meier curves corresponding to each MSKCC prognosis categories will be printed on a same graph.

If the number of patients who received IO in 2nd line is sufficient, following analysis will be performed according to MSKCC prognosis classification at Sunitinib initiation (good/intermediate/poor) using the Kaplan Meier method:

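### OS by MSKCC class at axitinib start is counted from the first sunitinib dose, so each time includes a death-free interval before classification

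*SAP*

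**What the plan says.** SAP 8.2.2, under secondary endpoints, states that "following analysis will be performed according to MSKCC prognosis classification at Axitinib initiation (good/intermediate/poor", using the Kaplan-Meier method. The list covers PFS under axitinib, ORR under axitinib and "OS for the sequence SU-AXI in the SU-AXI subgroup". For PFS and OS the three class curves go on one graph.

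The clock for that OS is set in SAP 6.1.2: "The OS will be defined as the time from date of first SU dose to the date of death of any cause". Its formulas all subtract the sunitinib start date, for example "Date of death reported in Long term Follow-up - Start date of Sunitinib + 1) / 30.44". Protocol 8.7.1 agrees: "OS is defined as the date from first SU dose to the date of death due to any cause".

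The class is a new measurement. The axitinib initiation visit in the protocol's CRF (Annex 1, section 4.1) has its own field, "MSKCC risk (second line line", separate from the first-line class.

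The population is conditioned on reaching axitinib. SAP 5.4 defines the SU-AXI subgroup thus: "It refers to all patients from the FAS receiving the combined SU-AXI sequence during the observation period". Protocol 8.5 expects it to comprise "two thirds of patients enrolled in the AXI 2nd line pool (approx. 225 patients"), whose sunitinib period is collected retrospectively.

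Neither document defines OS from axitinib start, a landmark analysis or delayed entry.

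**The concern.** A risk class recorded at the start of second line is naturally read as the outlook from that moment. A curve labelled poor risk at axitinib start will be taken as survival from axitinib start. As planned, it shows something else: time already lived on and after sunitinib, during which no member of the subgroup could die, plus survival after classification.

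Two things are at stake. The level of every class curve is too high for the reading it invites, and this carries into the median, the 3-monthly survival rates and the 24-month share alive that the SAP lists for OS. The contrast between classes is also affected, because it mixes prognosis at axitinib start with how long each class took to get there. SAP 6.4 lists duration of sunitinib treatment as a possible covariate when the baseline is axitinib initiation, so the plan itself treats prior sunitinib time as possibly prognostic. Here that time is built into the outcome.

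**Working it through.** **Design figures.** Protocol 8.5 reproduces: 525 × 0.68 = 357, 357 × 0.35 ≈ 125, and 225 + 125 = 350. The half-width at the median is 1.96 × √(0.25/350) = 0.052, the stated 5.2%. The point does not depend on this figure; it only fixes the population.

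**Identity.** For each patient in the subgroup:

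OS from sunitinib start = (axitinib start − sunitinib start) + OS from axitinib start.

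The first term contains no death, by selection into the subgroup. The class is measured at the end of that term.

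**Clock and class in the SAP's MSKCC time-to-event displays (8.2.2).**

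| Display | Class measured at | Time zero |
|---|---|---|
| PFS under axitinib | axitinib start | axitinib start |
| OS of the SU-AXI sequence | axitinib start | sunitinib start |
| PFS and OS for first-line sunitinib | sunitinib start | sunitinib start |

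The second row is the one whose class is measured after time zero.

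**Illustration 1: fixed gap.** Assumptions, none from the documents: exponential OS after axitinib with median m, and the same gap g (up to 24 months) for everyone.

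- 24-month OS from axitinib = 2^(−24/m)
- 24-month OS from sunitinib = 2^(−(24−g)/m)
- Median from sunitinib = g + m

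With g = 12:

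- Poor, m = 6: 2^(−4) = 6% becomes 2^(−2) = 25%; the median goes from 6 to 18 months.
- Good, m = 20: 2^(−1.2) = 44% becomes 2^(−0.6) = 66%; the median goes from 20 to 32 months.
- Ratio of medians: 20/6 = 3.3 becomes 32/18 = 1.8.

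With g from 6 to 18, the poor-class figure runs from 2^(−3) = 12% to 2^(−1) = 50%, and the good-class figure from 2^(−0.9) = 54% to 2^(−0.3) = 81%.

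**Illustration 2: varying gap (simulation).** Assumptions: exponential intervals, exponential post-axitinib OS with medians 24/16/8 months (good/intermediate/poor), no censoring.

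| Clock | Median OS, months | 24-month OS |
|---|---|---|
| From axitinib start | 24 / 16 / 8 | 50% / 35% / 12.5% |
| From sunitinib, median interval 6 | 33 / 25 / 17 | 65% / 53% / 31% |
| From sunitinib, median interval 9 | 38 / 30 / 21 | 70% / 60% / 42% |
| From sunitinib, median interval 12 | 43 / 34 / 24 | 75% / 66% / 50% |

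Medians rise by about 9 to 19 months and 24-month OS by about 15 to 38 percentage points.

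**Between-class contrast.** Cox hazard ratios, poor versus good, fitted to the same simulated patients on three time scales (one run, 2,000 per class, so the fits scatter around the true value):

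| True HR | Median interval, good / poor | Axitinib clock | Sunitinib clock | Sunitinib clock, delayed entry |
|---|---|---|---|---|
| 3 | 9 / 9 | 3.07 | 2.49 | 3.03 |
| 3 | 12 / 6 | 2.70 | 3.39 | 2.72 |
| 3 | 6 / 12 | 2.92 | 1.70 | 2.93 |
| 1 | 12 / 6 | 0.98 | 1.36 | 0.98 |
| 1 | 9 / 9 | 1.02 | 1.02 | 1.02 |

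On the sunitinib clock the contrast shrinks, grows or appears from nothing according to the interval pattern. Delayed entry returns the axitinib-clock value in each row, as it should when the post-axitinib hazard is constant.

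**The case against.** The best defence is that the plan does what it declares. The endpoint is labelled OS for the sequence, the protocol defines it from the first sunitinib dose, and SAP 5.4 assigns the sunitinib baseline to the sequence and the axitinib baseline to the axitinib period only. A reader might cite 5.4 as evidence that the SAP meant the other clock here; read in full, it does not say so. The unstratified sequence OS is a legitimate declared endpoint. The overstatement arises when the curves are read by a class that did not exist at time zero, but that is the reading a by-class display invites.

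Some stronger statements are tempting and do not hold:

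- **No curve can fall during the sunitinib period.** The death-free interval belongs to each patient. Intervals vary, so a curve can fall once the patients with the shortest intervals have reached axitinib.
- **This is the only display in the documents grouped by something learned after time zero.** That is true only among the SAP's MSKCC displays. Protocol 8.7.1 also plans PFS under axitinib by titration status, which needs a dose increase held for at least 4 weeks, and outcomes of the sequences by second-line drug.
- **Class differences are necessarily compressed.** This holds for a common gap, but the documents do not give the interval by class.
- **The sunitinib-start list is a clean comparator.** Its class and clock align. However, OS for first-line sunitinib is not limited to patients enrolled at sunitinib start, and about 225 of the planned 750 enter having already survived to axitinib.

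The limited consequence also stands. This is an additional display of a secondary endpoint in a descriptive, non-controlled study. SAP 4.2 says no test will be performed, although 8.1.2 plans log-rank comparisons; the curves and medians are affected either way.

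**Conclusion.** The mismatch is certain from the documents' own definitions. So is its consequence for level: read as survival by risk class at axitinib start, OS is too long in every class by each patient's own interval from sunitinib start to axitinib start. The direction and size of the distortion between classes cannot be settled from the documents.

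The numbers are illustrations resting on assumed exponential survival and assumed intervals. A reader might infer that the poor class suffers most. In the fixed-gap example that is so only in relative terms: 24-month OS rises by 19 points in the poor class and 22 in the good class, and both medians move by 12 months.

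A reader might also infer that the sequence OS endpoint itself is at fault. It is not challenged; the added fault is grouping it by a later class. No primary endpoint, sample size or safety result depends on this. It should still be corrected before the final analysis, because the display misleads as planned and the remedy is small.

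**What to change.** In SAP 8.2.2, for the analysis by MSKCC class at axitinib initiation, define OS as (date of death or last date known alive − start date of axitinib + 1)/30.44. Alternatively, keep the sunitinib clock and let patients enter the risk set at axitinib start. The first option answers the prognostic question directly.

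Leave the unstratified OS of the SU-AXI sequence as declared.

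If OS from sunitinib start is also wanted by MSKCC in the SU-AXI subgroup, use the first-line class at sunitinib initiation, which the CRF collects on both enrolment routes. That aligns class and clock but leaves the death-free interval in place. The display therefore needs delayed entry at axitinib start, or a label saying it is conditional on having reached axitinib.

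The cost is a short SAP edit and one derived variable. The dates needed are already collected, and there is no burden on patients or sites. Protocol 8.7 lets the SAP modify the plan and reserves protocol amendments for major changes to primary endpoints, which this is not. Reported OS by risk group will be shorter.

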8.2.3 Analyses of Axitinib Treatment

Axitinib treatment analyses will be provided in the safety population.

Proportion of patients with the recommended starting dose of AXI (5 mg BID) will be given with its 2-sided 95% 'exact' Clopper-Pearson confidence interval in the SU-AXI subgroup.

Same analysis will be done for the proportion of patients:

- With other Axitinib starting doses. A listing of other doses reported will also be given.
- For whom the dose was reduced
- For whom the dose was increased
- With temporary interruption during the AXI treatment period. Description of corresponding reasons will also be provided.

• With AXI discontinuation. Description of corresponding reasons will also be provided.

AXI total daily dose (mg) received over the AXI treatment period will be analyzed using descriptive statistics (mean, standard deviation, median and range).

Same analysis will be provided for:

- The dose intensity (%) of Axitinib
- Duration (days) of the first Axitinib interruption
- Duration (days) of all interruptions together

8.2.4 Analyses of Quality of Life Endpoints

Quality of life analyses will be provided in the FAS population on the SU-AXI subgroup. According to the questionnaire date, time windows will be derived according to the rule explain in section **Error! Reference source not found.** In case of missing or partial date, questionnaires will not be analyzed.

Quality of life will be analyzed using descriptive statistics at the treatment initiation, on the first 6 months and on AXI discontinuation overall and according to the best response observed under Axitinib treatment (CR, PR, SD, and PD):

- the FKSI-19 global score,
- the FKSI DRS-P subscore,
- the FKSI DRS-E subscore,
- the FKSI TSE subscore,
- the FKSI FWB subscore,
- the SF36 MH subscore,
- and the SF36 RE subscore.

Same analysis will be repeated on changes in scores/subscores from Baseline.

In order to explore possible variations in time and the possible differences according to the best response observed under Axitinib treatment, each changes in scores/subscores mentioned above will be analyzed using a mixed model for repeated measures (MMRM) according to the method described in section 8.1 of this document (Analysis of longitudinal data).

Estimated mean changes in scores/subscores from baseline will be provided and represented graphically with their 95% confidence interval:

- monthly (on the first 6 months),
- for each best response observed under Axitinib treatment (CR, PR, SD, and PD),
- in case of a statistically significant interaction between time and best response observed under Axitinib treatment, monthly estimated means will also be provided according to best response observed under Axitinib treatment (CR, PR, SD, and PD)

